## **5. ANALYSIS SETS**

### **5.1. Definition**

#### **5.1.1. Enrolled Set**

The enrolled set will comprise all subjects who signed an ICF, whether randomized/vaccinated or not.

#### **5.1.2. Randomized Set**

The randomized set will include all subjects documented as randomized in the randomization system (SBIR).

#### **5.1.3. Exposed set**

The Exposed Set (ES) will include all subjects with at least one vaccine administration documented:

- A safety analysis based on the ES will include all vaccinated subjects.
- An immunogenicity analysis based on the ES will include all vaccinated subjects for whom immunogenicity results are available.

The ES analyses will be performed per effective treatment group (corresponding to the actually administered priming sequence).

### 5.1.4. Per-Protocol set for analysis of immunogenicity

The Per-Protocol set will be adapted by timepoint to include all eligible subjects' data up to the time of important protocol deviation, namely:

- Dose of study vaccine not according to protocol procedures and to their random assignment.
- Randomization code broken.
- Non-compliance with the procedures and intervals defined in the protocol.
- Intake of concomitant medication/product/vaccination leading to elimination from the Per-Protocol analysis.
- Occurrence of medical condition leading to elimination from the Per-Protocol analysis (refer to Section 6.7.2 of the protocol).

## 5.2. Criteria for eliminating data from Analysis Sets

Elimination codes are used to identify subjects to be eliminated from analysis. Details are provided below for each set.

### 5.2.1. Elimination from Exposed Set (ES)

Code 1030 (Study vaccine not administered at all) and code 900 (invalid informed consent or fraud data) will be used for identifying subjects eliminated from ES.

### 5.2.2. Elimination from Per-protocol analysis Set (PPS)

#### 5.2.2.1. Excluded subjects

A subject will be excluded from the PPS analysis under the following conditions:

Code	Decode → Condition under which the code is used
900	Invalid informed consent or fraudulent data → Invalid informed consent or fraudulent data.
1030	Study vaccine not administered at all but subject number allocated → Subject randomized but not vaccinated.
1060	Randomization code was broken → The randomization code was broken at the investigator site or GSK safety department
2010	Protocol violation (inclusion/exclusion criteria) including age → ineligible subject
2020	Unknown baseline anti H1-stalk antibody titer by ELISA → Unknown baseline anti H1-stalk antibody titer by ELISA.

#### 5.2.2.2. Right censored Data

Data from visit X and subsequent visit will be censored for the PPS analysis under the following conditions. The code \*\*\*.Vx will be used to identify subjects whose immunogenicity data should be eliminated from a specific visit onwards.

Code	Decode → Condition under which the code is used
1040.Vx	Administration of concomitant vaccine(s) forbidden in the protocol → Administration of a vaccine not foreseen in the protocol during the period starting 30 days before the first study vaccine (Visit 1) up to the blood sampling at Day 85 (Visit 6) and in the period starting 30 days before the booster dose at Month 14 (Visit 8) up to the blood sampling at Month 14+28 days (Visit 10). → Influenza vaccination at any time during study period
1070.Vx	Vaccination not according to protocol → 

Incomplete vaccination course before treatment withdrawal

Subject was vaccinated with the correct vaccine but containing a lower volume

Wrong replacement or study vaccine administered (not compatible with the vaccine regimen associated to the treatment number)

Route of the study vaccine is not intramuscular

Wrong reconstitution of administered vaccine

1080.Vx	Vaccine temperature deviation → vaccine administered despite a Good Manufacturing Practices (GMP) no-go temperature deviation
1090.Vx	Expired vaccine administered → expired vaccine administered
2040.Vx	Administration of any medication forbidden by the protocol → 

Any investigational or non-registered product (drug or vaccine) other than the study vaccines used during the study period.

Immunosuppressants or other immune-modifying drugs administered chronically (i.e., more than 14 days) during the study period.

Immunoglobulins and/or any blood products administered during the study period

Administration of long-acting immune-modifying drugs during the study period.

2060.Vx	Intercurrent medical condition → Intercurrent medical condition that has the capability of altering immune response, or alteration of initial immune status (suspected or confirmed immunosuppressive or immunodeficient condition) which may influence immune response → Intercurrent H1N1 Influenza infection (RT PCR confirmed)
2080.Vx	Subjects did not comply with vaccination schedule → Subjects that did not comply with the vaccination interval (including unknown dates): subjects for whom the dose 1→dose 2 is outside [56-66 days] subjects for whom the dose 2→dose 3 is outside [336-364 days]

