## 2. STUDY DESIGN

\*If a subject presents signs and symptoms of influenza-like illness (ILI), nasal and throat swabs will be collected as soon as possible (preferably within 24 hours, but not later than 7 days) after the onset of an ILI to test for influenza and/or other respiratory pathogens by RT-PCR **if deemed necessary or for storage**.

\*\*IDMC reviews will be performed throughout the study.

- **Experimental design:** Phase I/II, observer-blind, randomized, controlled, multi-centric study with 10 parallel groups.
- **Study groups:**
  - **cH8/P/cH5-AS03 group:** 47 subjects receiving one dose of cH8/1N1+AS03 at Day 1, one dose of PBS at Day 57 and one booster dose of cH5/1N1+AS03 at Month 14.
  - **cH5/P/cH8-AS03 group:** 47 subjects receiving one dose of cH5/1N1+AS03 at Day 1, one dose of PBS at Day 57 and one booster dose of cH8/1N1+AS03 at Month 14.
  - **cH8/5/11-AS03 group:** 47 subjects receiving one dose of cH8/1N1+AS03 at Day 1, one dose cH5/1N1+AS03 at Day 57 and one booster dose of cH11/1N1+AS03 at Month 14.
  - **cH8/P/cH5-AS01 group:** 47 subjects receiving one dose of cH8/1N1+AS01 at Day 1, one dose of PBS at Day 57 and one booster dose of cH5/1N1+AS01 at Month 14.
  - **cH5/P/cH8-AS01 group:** 47 subjects receiving one dose of cH5/1N1+AS01 at Day 1, one dose of PBS at Day 57 and one booster dose of cH8/1N1+AS01 at Month 14.
  - **cH8/5/11-AS01 group:** 47 subjects receiving one dose of cH8/1N1+AS01 at Day 1, one dose cH5/1N1+AS01 at Day 57 and one booster dose of cH11/1N1+AS01 at Month 14.
  - **cH8/P/cH5 group:** 47 subjects receiving one dose of cH8/1N1 at Day 1, one dose of PBS at Day 57 and one booster dose of cH5/1N1 at Month 14.
  - **cH5/P/cH8 group:** 47 subjects receiving one dose of cH5/1N1 at Day 1, one dose of PBS at Day 57 and one booster dose of cH8/1N1 at Month 14.
  - **cH8/5/11 group:** 47 subjects receiving one dose of cH8/1N1 at Day 1, one dose cH5/1N1 at Day 57 and one booster dose of cH11/1N1 at Month 14.
  - **IIV4 group:** 47 subjects receiving one dose of *Fluarix Quadrivalent* at Day 1, one dose of PBS at Day 57 and one dose of *Fluarix Quadrivalent* at Month 14.
- **Treatment allocation:** randomized (1:1:1:1:1:1:1:1:1 ratio) using GSK Biologicals' Randomization System on Internet (SBIR). The randomization algorithm will use a minimization procedure accounting for center, sex, age (18-30 years vs. 31-39 years) and history of influenza vaccination since the 2014/2015 season (yes vs. no).

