Passive surveillance will be carried out from Visit 1 (after Dose 1) until the end of the study (Visit 12). Subjects will be instructed to contact the investigator/study staff as soon as they experience ILI symptoms. During the entire study period, nasal and throat swabs will be collected as soon as possible (preferably within 24 hours, but not later than 7 days) after the onset of an ILI to test for influenza and/or other respiratory pathogens by RT-PCR *if deemed necessary, or stored for future research.*

All cases of ILI have also to be recorded as unsolicited adverse event (AE) or serious adverse event (SAE) in the electronic Case Report Form (eCRF).

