### **6.3.2. Additional considerations**

- In addition, the percentage of subjects with at least one local AE (solicited and unsolicited), with at least one general AE (solicited and unsolicited) and with any AE with causal relationship to vaccination during the solicited follow-up period will be tabulated with exact 95% CI. The same calculations will be repeated for grade 3 AEs with causal relationship to vaccination.
- The percentage of subjects reporting each individual solicited local and general grade  $\geq 2$  AE during the solicited follow-up period will be tabulated with exact 95% CI. The same tabulation will be performed for grade  $\geq 2$  and grade 3 AEs with causal relationship to vaccination, and for AEs with a medically attended visit.
- The overall number of days with symptoms will be summarized by dose and by symptom, using summary statistics.
- The percentage of subjects with at least one report of unsolicited grade 3 AE with causal relationship to vaccination reported up to 28 days after vaccination will be tabulated with exact 95% CI
- The percentage of subjects with at least one report of unsolicited AE requiring medical attention during the 28 days after vaccination will be tabulated with exact 95% CI. The tabulation will be repeated for the grade 3, related, and grade 3 related events. The same analysis will be provided for the events reported within 28 days post-vaccination.
- The percentage of subjects with episode(s) of grade 3 ILI (any, RT-PCR-confirmed) will be summarized by group with exact 95% CI.

- A summary of subjects with all combined solicited (regardless of their duration) and unsolicited AEs will be provided. Solicited AEs will be coded by MedDRA (using the latest version) as per the following codes:

Solicited symptom	Lower level term code
Pain at injection site	10022086
Redness at injection site	10022061
Swelling at injection site	10053425
Fever	10016558
Headache	10019211
Fatigue	10016256
Gastrointestinal symptoms	10017944
Arthralgia	10003239
Myalgia	10028411
Shivering	10040558

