PRE = pre-vaccination; P1 = post-dose 1; PII = post-dose 2; PIII = post-dose 3 (booster); D = day; M = month; ELISA = enzyme-linked immunosorbent assay; MN = microneutralization; IIV4 = quadrivalent inactivated influenza vaccine; ICS = intracellular cytokine staining

\*CMI sub-cohort comprising ~225 Phase II subjects.

In case of insufficient blood sample volume to perform assays for all antibodies, the samples will be analyzed according to priority ranking provided in [Table 2](#).

- **Influenza-like illness (ILI) surveillance:** ILI is defined as at least one of these systemic symptoms:

- Temperature (oral)  $\geq 37.8^{\circ}\text{C}/98.6^{\circ}\text{F}$  and/or,
- Myalgia (widespread muscle ache);

AND at least one of these respiratory symptoms:

- Cough and/or,
- Sore throat.

Passive surveillance will be carried out from Visit 1 (after Dose 1) until the end of the study (Visit 12). Subjects will be instructed to contact the investigator/study staff as soon as they experience ILI symptoms. During the entire study period, nasal and throat swabs will be collected as soon as possible (preferably within 24 hours, but not later than 7 days) after the onset of an ILI to test for influenza and/or other respiratory pathogens by RT-PCR.

All cases of ILI have also to be recorded as unsolicited adverse event (AE) or serious adverse event (SAE) in the electronic Case Report Form (eCRF).

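### After a code break, section 5.2.2.1 (code 1060) removes the subject's whole per-protocol record, while section 5.1.4 keeps the data collected before the break

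*SAP*

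**What the plan says.** All references are to the current SAP (Amendment 3).

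**Code break.** Section 5.1.4 adapts the PPS by timepoint, keeping "data up to the time of important protocol deviation". Its list of deviations includes a broken randomization code. Section 5.2.2.1 lists the conditions that exclude a subject altogether. Code 1060 is one of them, with the condition "The randomization code was broken at the investigator site or GSK safety department" and no visit suffix. Section 5.2.2.2 holds the codes that carry a .Vx suffix and act only forward in time: "Data from visit X and subsequent visit will be censored for the PPS analysis under the following conditions".

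**ILI testing.** Code 2060.Vx in section 5.2.2.2 censors from the affected visit onward for "Intercurrent H1N1 Influenza infection (RT PCR confirmed"). The surveillance text in section 2 now has swabs tested "if deemed necessary, or stored for future research", and the footnote to the design figure says "if deemed necessary or for storage". Section 6.3.2 still plans this summary: "The percentage of subjects with episode(s) of grade 3 ILI (any, RT-PCR-confirmed) will be summarized by group with exact 95% CI".

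**The concern.** The PPS is the primary set for immunogenicity (section 6.2.1), so its membership should not depend on which section the programmer reads. A code break can happen at any time up to Month 26. Under section 5.2.2.1 a late break reaches back and removes samples drawn months before anyone was unblinded.

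Two things are at stake:

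- Day 29 and Day 85 results feed the primary immunogenicity endpoints (section 4.1) and the adjuvant decision rule (section 7).
- Section 8.2 presents the interim analyses as delivering final results for their timepoints. If a code is broken after the Day 85 interim analysis, the same Day 85 table would be produced on a smaller set at the final analysis. Section 8.1 marks the interim as internal and the final analysis as the one for the study report and public posting.

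The RT-PCR wording is a smaller matter. A PPS code and a safety summary both rest on a laboratory result that is no longer obtained routinely.

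**Working it through.** The plan gives no figure to reproduce. The check sets the rules side by side and counts visits.

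**1. Which rule does each deviation in section 5.1.4 get?**

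| Deviation type in 5.1.4 | Code(s) | Effect |
|---|---|---|
| Dose not per protocol or assignment | 1070.Vx (also 1080.Vx, 1090.Vx) | right-censored |
| Procedures and intervals | 2080.Vx, 2090.Vx | right-censored / visit-specific |
| Concomitant product or vaccine | 1040.Vx, 2040.Vx | right-censored |
| Medical condition | 2060.Vx | right-censored |
| Randomization code broken | 1060 | whole subject excluded |

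Only the code break is treated differently from what section 5.1.4 describes. The other whole-subject codes in section 5.2.2.1 (900, 1030, 2010, 2020) concern consent or fraud, non-vaccination, eligibility and a missing baseline titer. These cannot sensibly be applied from a timepoint onward.

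**2. What does each rule keep?** Section 2 gives eight serology visits: 1 (Day 1), 3 (Day 29), 6 (Day 85), 7 (Month 8), 8 (Month 14), 10 (Month 14 + 28 days), 11 (Month 20) and 12 (Month 26).

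| Break falls between | Kept under 5.1.4 | Kept under 5.2.2.1 |
|---|---|---|
| Visits 3 and 6 | 2 (Visits 1, 3) | 0 |
| Visits 6 and 7 | 3 (Visits 1, 3, 6) | 0 |
| Visits 10 and 11 | 6 (Visits 1, 3, 6, 7, 8, 10) | 0 |

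**3. Does this reach the adjuvant rule?** Template 37 uses Day 29 for the one-priming-dose groups and Day 85 for the two-dose groups. Under section 5.2.2.1, a break after Visit 3 in a one-dose group, or after Visit 6 in a two-dose group, removes an observation that section 5.1.4 would keep.

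**4. Size per break.** One subject in a planned group of 47 is 1/47 = 2.1%. The adjuvant comparison pools three groups per arm, 3 × 47 = 141, so one subject is 1/141 = 0.7% of an arm.

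**5. RT-PCR.** In SAP Amendment 2 the swab text ended without a condition: swabs were taken "after the onset of an ILI to test for influenza and/or other respiratory pathogens by RT-PCR". The current version adds the condition. It also removes the RT-PCR-confirmed split from section 6.3.1 but leaves it in section 6.3.2. No PPS rule addresses an ILI episode without a result.

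**The case against.** **On code 1060.** Section 5.2 announces that it gives the details for each set, so the specific table could be taken to govern. On that view the programmer has a clear instruction: exclude. Template 3 counts code 1060 at each analysis, so any change would be visible. Section 6.2.1 adds an Exposed Set analysis if 5% or more of vaccinated subjects are eliminated at a timepoint.

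Part of this stands: the effect per break is small and would be visible. But a section that supplies details should carry out the definition, and here it reverses it for one deviation only. The Exposed Set analysis does not settle which PPS rule applies, and one break will not trigger it: 5% of 470 is 23.5, so it takes 24 eliminated subjects overall. If the 5% were read within a group, 5% of 47 is 2.35, so three.

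**On RT-PCR.** A reader might infer that code 2060.Vx contradicts optional testing, that section 6.3.2 counts untested episodes as negative, or that selective testing biases the group comparisons. The documents do not support these readings:

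- Both rules can be followed: confirmed infections are censored, and untested ones are not.
- The section 6.3.2 denominator is not stated. Section 12.2.5 treats subjects without a reported event as event-free, which leaves the negative reading open. Template 46, however, has a separate row for swabs without a result and bases its percentages on swabs with one.
- Conditional testing came with Protocol Amendment 4 (11 July 2019; SAP 12 September 2019), so the effect should fall mainly on later ILI.
- The trial is observer-blind, and apart from the unblinded statistician or analyst the sponsor's study personnel stay blinded at the interim analyses (section 8.1). Nothing shows that testing would favor one arm.
- Retaining the section 6.3.2 line may simply allow results already obtained to be reported.

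**Conclusion.** The code-break point holds: sections 5.1.4 and 5.2.2.1 give incompatible rules for the same event, in the primary immunogenicity set. The illustrative break between Visits 10 and 11 gives six of eight serology visits against none. The size is one subject per break, 2.1% of a planned group of 47, with no stated direction of bias. The number of code breaks is not known from the SAP. A reader might infer that breaks mostly follow safety events and so select particular subjects. The SAP names the safety department only as one place where a code may be broken and says nothing about frequency or cause.

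The RT-PCR point stands only as a secondary clarification. Its effect on titers cannot be sized from the documents, which give neither an attack rate nor a fold rise after infection. They give no ground to stop censoring confirmed H1N1 infections.

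**What to change.** 1. Delete code 1060 from section 5.2.2.1 and add it to section 5.2.2.2 as 1060.Vx, with X the first visit after the break. This brings the elimination table into line with section 5.1.4 and keeps Day 29 and Day 85 results that precede the break. Template 3 already lists 1060 together with the visit-specific codes and needs no new row.
2. Leave code 2060.Vx as it is. In section 6.3.2, state that ILI episodes without an RT-PCR result are shown as a separate category and are not counted as not confirmed.

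The first change costs SAP wording and elimination-code programming. The second costs one sentence and one extra category in a descriptive table. Neither needs additional samples or testing.

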### 5.2.2.3. Visit-specific censored Data

Data at visit X will be censored for the PPS analysis under the following conditions. The code \*\*\*.Vx will also be used to identify study withdrawal at visit X.

Code	Decode → Condition under which the code is used
2090.Vx	Subjects did not comply with immunological blood sample schedule → 

phase II subjects for whom the dose 1→visit 2 blood sample is outside [7-9 days]

subjects for whom the dose 1→visit 3 blood sample is outside [28-38 days]

phase II subjects for whom the dose 2→visit 5 blood sample is outside [7-9 days]

subjects for whom the dose 2→visit 6 blood sample is outside [28-38 days]

subjects for whom the dose 2→visit 7 blood sample is outside [168-196 days]

subjects for whom the dose 2→visit 8 blood sample is outside [336-364 days]

phase II subjects for whom the dose 3→visit 9 blood sample is outside [7-9 days]

subjects for whom the dose 3→visit 10 blood sample is outside [28-38 days]

subjects for whom the dose 3→visit 11 blood sample is outside [168-196 days]

subjects for whom the dose 3→visit 12 blood sample is outside [336-364 days]

2100.Vx	Serological results not available post-vaccination → No immunological result at all for the specific blood sample collection timepoint
2120.Vx	Obvious incoherence or abnormality or error in data → Unreliable released data as a result of confirmed sample mismatch or confirmed inappropriate sample handling at lab

### **5.3. Protocol deviation not leading to elimination from per-protocol analysis set**

Important protocol deviations not leading to elimination from the Per-Protocol set for immunogenicity will be reported by groups. The full list of reportable protocol deviations is available in the study protocol deviation management plan.

### **5.4. Selection of samples for the passive transfer experiment**

The samples to be considered for the passive transfer experiment will be the samples from the compliant subjects at the time point of interest, based on the elimination codes defined in Section 5.1.4 for the PPS for the analysis of immunogenicity. The selection of samples to be considered for the passive transfer experiment will be done based on the information available at the time of the experiment (just before the experiment). It will be made sure that the selection of sample is posterior to:

- All subjects having completed the visit associated to the passive transfer experiment timepoint;
- The shipment and reconciliation of the serum samples.

## **6. STATISTICAL ANALYSES**

All analyses will be performed using SAS.

Note that standard data derivation rules and stat methods are described in Annex 1 and will not be repeated below.

### **6.1. Demography**

#### **6.1.1. Analysis of demographics/baseline characteristics planned in the protocol**

Demographic characteristics (center, age at study vaccination in years, gender, ethnicity, geographic ancestry, history of influenza vaccination since the 2014/2015 season) and withdrawal status will be summarized by group in the ES, using descriptive statistics:

- Frequency tables will be generated for categorical variable such as center.
- Mean, median, standard deviation will be provided for continuous data such as age.

#### **6.1.2. Additional considerations**

Country, age category, weight, height, Body Mass Index (BMI) and medical history (by System Organ Class (SOC)) will be summarized with the other demography/baseline characteristics. The demographic characteristics will also be provided for the Randomized set and Per Protocol set.

Reason for withdrawal and reason for eliminating data from the PPS will be summarized by group. The size of the PPS will also be presented by visit.

## 6.2. Immunogenicity

### 6.2.1. Analysis of immunogenicity planned in the protocol

The analysis of immunogenicity will be performed primarily on the PPS. If 5% or more of the vaccinated subjects are eliminated from the PPS at one timepoint, a second analysis will be performed on the ES.

### 6.2.2. Within group assessment

#### 6.2.2.1. Humoral immunogenicity assessment

For each study group, at each timepoint at which the tests are done and results are available, for each humoral immunity parameter, the following analyses will be performed:

- Seropositivity rates and GMTs, with exact 95% CI.
- MGI from Day 1, with 95% CI.
- MGI at Visits 10, 11 and 12 from Day 29 (=Visit 3), Day 85 (=Visit 6), Month 14 (=Visit 8), with 95% CI.
- Percentage of subjects with at least 4-fold increase from Day 1, with exact 95% CI (not applicable for HI test).
- Percentage of subjects with at least 10-fold increase from Day 1, with exact 95% CI (not applicable for HI test).
- Seroprotection rate (SPR) (only for HI test).
- Seroconversion rate (SCR) (only for HI test).
- Distribution of antibody concentrations using reverse cumulative distribution curves (only for ELISA test).

The correlation between anti-H1 HA stalk ELISA and anti-H1 HA stalk MN assay results will be explored.

